3 THEORETICAL FRAMEWORK

Aetiology of neonatal sepsis

Neonatal sepsis is commonly defined as a severe systemic infection occurring in the neonatal period. Early-onset neonatal sepsis (EOS) refers to those infections presenting within 72 hours of life and is usually the result of vertical acquisition of the pathogen. This is in contrast to late-onset neonatal sepsis which presents after 72 hours of life usually results from horizontal acquisition of the pathogen (i.e. from the neonate's environment)(26).

Many risk factors are common to both early- and late-onset sepsis, but their importance differs for each of the conditions. EOS relates more to maternal risk factors(26–29), and LOS to neonatal factors(26,27,29). Environmental factors will also influence the risk of LOS, as they will affect the risk of horizontal transmission of pathogens(26,27). As this study aims to create a risk stratification system relevant for low-resource settings, it is important to consider patient-

Using machine learning to model early-onset neonatal sepsis risk in Uganda (NeoRisk)

reportable or easily measurable factors that may modify the risk of neonatal sepsis. These have been considered systematically by examining possible related maternal, neonatal, and environmental factors and their associations.

Patient-reportable risk factors

To assess many of the established risk factors for neonatal sepsis, mothers must receive skilled antenatal and delivery care; for example, a diagnosis of chorioamnionitis would require assessment by a midwife or doctor and may also require measuring of vital signs and laboratory tests to confirm the diagnosis. As the purpose of this project is to statistically model risk factors for early-onset neonatal sepsis with the aim to help inform clinical decision making in a low-resource setting, it is necessary to consider the association between neonatal sepsis and factors which are either patient-reportable or easily measurable without the need for laboratory or radiological services that may be unavailable in these settings.

Therefore, in designing the data collection instrument for this study, we have considered which patient-reportable factors might be strongly associated with the established sepsis risk factors above, and determined the following fields for data collection, listed in the table below:

Category	Risk factor	Data collection field	Established	Investigational
Maternal factors prior to pregnancy	Age	(years)	X	
	Tribe			X

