	Medical comorbidities increasing infection risk			
	HIV		X	
	Chronic infection e.g. hepatitis, tuberculosis		X	
	Regular immunosuppressive medications e.g. steroids		X	
	Previous abdominal surgery			X
	Obstetric history		X	
	Number of previous pregnancies		X	
	Number of previous live deliveries			X
Low socioeconomic status	Number of previous neonatal deaths		X	
	Maternal and partner's occupation			X
	Location of dwelling			X
	Construction of dwelling			X
	Occupancy of dwelling, including number of adults, children, and animals			X

Using machine learning to model early-onset neonatal sepsis risk in Uganda (NeoRisk)

	Source of lighting		x
	Maternal and partner's educational level		x
	Cooking facilities at home e.g. open fire indoors, gas stove		x
	Access to refrigeration at home		x
	Food insecurity		x
	Presence or absence of debt		x
	Water, sanitation and hygiene	x	
	Type of sanitation available at home (type of toilet/latrine)		x
	Source of drinking water		x
	Access to handwashing facility at home		x
	Nutritional status	x	
	Mid upper arm circumference	x	
	BMI	x	
	Dietary quality		x
	Substance use	E.g. recreational drugs, smoking, alcohol	x
Maternal factors during pregnancy	Vaginal colonisation		x
	Abnormal discharge during pregnancy		x
	Vulval or vaginal discomfort/pruritus		x
	Dyspareunia or postcoital bleeding		x
	Regularity of menstrual cycle		x
	Urinary tract symptoms during pregnancy	x	
	Diarrhoea or vomiting during pregnancy	x	
	Access to sanitation at home		x
	Antibiotic use during pregnancy		x
	Invasive procedures during or prior pregnancy e.g. cervical cerclage, surgical termination of pregnancy		x
	Insufficient or late antenatal care		x
	Number of antenatal appointments attended		x
	Number of antenatal ultrasound scans		x
	Screening blood tests taken antenatally		x

Using machine learning to model early-onset neonatal sepsis risk in Uganda (NeoRisk)

Using machine learning to model early-onset neonatal sepsis risk in Uganda (NeoRisk)

Low APGAR scores		X	
Clinical signs of sepsis or meningitis within first 72h of life		X	
	Temperature instability	X	
	Poor feeding	X	
	Lethargy	X	
	Jaundice at <24h of life	X	
	Respiratory distress	X	
	Tachycardia	X	
	Tachypnoea	X	
	Poor perfusion	X	
	Abnormal tone	X	
Umbilical cord care	e.g. application of herbal remedies		X
Method of feeding	Breast versus formula	X	
	Water used to make up formula (e.g. filtered, tap)		X

Diagnosis of neonatal sepsis

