4.2 Outcome

- Primary outcome for Phase 1: Positive blood culture amongst neonatal participants
- Primary outcome for Phase 3: Clinician (specialist neonatal or paediatric doctor) diagnosis of sepsis amongst neonatal participants as documented in clinical notes or discharge letter
- Clinical features of neonatal sepsis as listed in GAIA neonatal infections case definition
- Admission to neonatal unit
- Readmission to hospital in first 28 days amongst neonatal participants
- Death before 28 days of age
- Sensitivity, specificity, positive and negative predictive value of risk stratification model for participants in Kampala and Harare

Using machine learning to model early-onset neonatal sepsis risk in Uganda (NeoRisk)

5 STUDY DESIGN and METHODS of DATA COLLECTION AND DATA ANALYSIS

There will be three main phases to this study, which is an observational cohort study.

Using machine learning to model early-onset neonatal sepsis risk in Uganda (NeoRisk)

Phase 1 will take place at Kawempe Hospital in Kampala, Uganda. Participants will be recruited from labour wards by study staff, and interim analysis will be completed after recruitment of 10% of the total sample. See section 7.3 for further details.

Data will be collected via an online CRF, including the factors listed in the table in Section 3.

Additionally:

- All neonates within the study will have a **neonatal venous blood sample** taken for culture by designated study staff
 - This must be taken before administration of antibiotics or within 48 hours of birth, whichever is sooner, and regardless of whether the neonate is being investigated and treated for sepsis.
- **Postnatal information** will be collected via telephone at 1 month including maternal and infant outcome, hospital readmission or clinical illness, and vaccines given

All data will be checked for quality control by a member of the study team.

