A blood culture will be taken from all neonatal participants at birth, prior to starting antibiotic treatment wherever safe to do so. The volume of blood taken for culture must be 1-2ml and will be verified by weighing blood culture bottles. Training will be provided to paediatric and study teams on blood culture sampling methods, including adequate cleaning of the skin prior to sampling. Feedback on sample volumes and contamination rates (see section 7.3 for definition) will be fed back to paediatric consultants, and additional staff training offered. Where sample is remaining after 3ml is added to the culture bottle, the excess will be retained as a blood spot sample for use in future ethically approved research, where the participant has consented to this.

The results of the microbiological tests will be communicated to the participant's clinical team in real time – see section 7.3.4 for further details. Clinician diagnosis of sepsis will be recorded where a clinician of registrar level or above has recorded a diagnosis of sepsis within 48 hours of birth. To reduce the subjectivity of this measure, GAIA level of certainty for a diagnosis of sepsis will also be assessed (35) and the level of diagnostic certainty recorded (1-5, as per GAIA criteria). Medical records are recorded on paper at Kawempe Hospital, before being coded into an electronic medical record by data clerks. PDF scans of medical records will be available where detailed review is required.

All participant data will be collected by trained study staff, and recorded into an online CRF hosted on REDCap, a secure web application. No patient identifiable data will be stored on the main REDCap database. See section 8.6 for further details of data management plans.

The postnatal information will be completed via a telephone call at 28 days post-delivery, made by study staff. Participants' contact number, a contact number for their partner, and a contact number for a second friend or family member will be taken at recruitment to minimise loss to follow up due to changes to mobile telephone number. Participant identity will be confirmed using three factors (date of birth, full name, address/village). The following information will be collected:

- Health status of mother and baby
- Any visits to medical care for the neonate
 - If attended or admitted to Kawempe hospitals, these electronic medical records will be reviewed by study staff

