The focus groups will be conducted by members of MUJHU's social sciences team and [name]. A tool has been developed by the social sciences team and [name] for these discussions (see attached). The discussions will be recorded, and recordings destroyed once the discussions have been transcribed. The social sciences team will then complete thematic analysis of the discussions.

We anticipate Phase 1 will take place between January and July 2024.

Phase 2 will use the data collected in phase 1 to construct a risk stratification model, in collaboration with the Advanced Research Computing Centre at University College London.

We anticipate Phase 2 will take place between March and September 2024.

Using machine learning to model early-onset neonatal sepsis risk in Uganda (NeoRisk)

Phase 3 will involve external validation of the risk stratification tool. This phase will take place at Sally Mugabe Central Hospital in Harare, Zimbabwe. Participants will be recruited from antenatal clinics and labour wards by study staff.

The same data will be collected from participants in Phase 3 as in Phase 1. Ideally, data collection will take place via the Neotree platform(41) – this will be decided once the factors included in the model have been determined, and whether they are already in routine collection via Neotree. If the Neotree platform will not capture sufficient data to match the inputs of the model, an online CRF will be created as in Phase 1 via REDCap. This decision will be made in collaboration with the local study team prior to the start of recruitment.

The primary outcome for Phase 3 will be senior clinician diagnosis of sepsis recorded within 48 hours of delivery, and blood cultures (when available) will only be taken in neonates judged to be at risk of, or with clinical signs of sepsis as per standard clinical guidelines. Using senior clinician diagnosis of sepsis as the outcome is because supply of blood culture bottles and laboratory analysis of cultures is unreliable and is unlikely to be available to all study participants as in the Phase 1 setting. The risk stratification model will be applied to these data to determine its accuracy in a second population and explore its generalisability.

We anticipate Phase 3 will take place between September 2024 and March 2025.

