11. APPENDICES

11.1 Appendix 1

Schedule of Procedures				
Procedures	Visits (insert visit numbers as appropriate)			
	Screening	Antenatal	Delivery	1 Month
Informed consent	x			
Completion of relevant CRF		x	x	x
Blood culture (neonatal)			x	
Blood spot for PCR (neonatal)			x	
Follow up (telephone)				x

11.2 Appendix 2

Amendment Log				
Amendment No.	Protocol version no.	Date issued	Author(s) of changes	Details of changes made
1	2.1	09.02.2024		Clarification on focus group rationale; see section 5

11.3 Appendix 3

Complete the form below. It will require review and sign-off by the Institute Director (SGUL) or the Care Group Lead (SGHFT).

Research Data Protection Impact Assessment (DPIA)

Using machine learning to model early-onset neonatal sepsis risk in Uganda (NeoRisk)

Data Protection Impact Assessments (DPIAs) are a tool which can help organisations identify the most effective way to comply with their data protection obligations under the Data Protection Act 2018 (DPA 18) and meet individuals' expectations of privacy.

A DPIA helps identify data privacy risks when planning new, or revising existing, projects and to identify actions to mitigate these risks. In the rare cases where risks cannot be mitigated at all it may be necessary to consult with the Information Commissioner's Office (ICO). Under data protection legislation it is a legal requirement to complete a DPIA in the following circumstances:

[figure not shown]
- where data processing is likely to result in a high risk of harm to individuals, e.g. new, invasive technology is proposed
- when large volumes of personal data are processed, e.g. use of behavioural profiles based on website usage
- when processing special category personal data on a large scale, e.g. healthcare data, genetic tests to assess and predict the disease/health risks
- where publicly accessible areas are monitored, e.g. CCTV or when filming public areas

Therefore a DPIA will be carried out for both internal and partnership projects which require the collection/processing of personal data in any format for the purpose of research.

The DPIA should be carried out towards the start of the project, in order to identify any associated information risks and mitigate in the early stages, before you start processing.

Study Title/Acronym:	Using machine learning to model early-onset neonatal sepsis risk in Uganda
JRES Reference Number:	TBD
Chief Investigator Name:	[REDACTED]
Chief Investigator Email Address:	[REDACTED]

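### Clinician-diagnosed sepsis is counted only to 48 h in Section 5 and without limit in Section 4.2, although the protocol defines early-onset sepsis by 72 h

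*Combined protocol and SAP*

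**What the plan says.** - **Target condition (Section 3).** "Early-onset neonatal sepsis (EOS) refers to those infections presenting within 72 hours of life". It is contrasted with "late-onset neonatal sepsis which presents after 72 hours of life". The data-collection table in the same section lists "Clinical signs of sepsis or meningitis within first 72h of life".
- **Phase 1 clinician diagnosis (Section 5).** It is recorded where "a clinician of registrar level or above has recorded a diagnosis of sepsis within 48 hours of birth". Section 3 makes clinical diagnosis a secondary outcome; the Phase 1 primary outcome in Section 4.2 is a positive blood culture.
- **Phase 3 primary outcome (Section 5).** "The primary outcome for Phase 3 will be senior clinician diagnosis of sepsis recorded within 48 hours of delivery".
- **Phase 3 primary outcome (Section 4.2).** A specialist in neonatology or paediatrics must have made the "diagnosis of sepsis amongst neonatal participants as documented in clinical notes or discharge letter". No time limit is given.

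The grade is therefore a specialist doctor in Section 4.2, a registrar or higher for Phase 1 in Section 5, and a senior clinician for Phase 3 in Section 5. No section explains why a 48 h window is used for a 72 h condition. The 28-day call and the review of hospital records collect later illness, but no rule uses them to classify early-onset sepsis.

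**The concern.** The model is meant to predict early-onset sepsis as the protocol defines it. In Phase 3 the clinician diagnosis is the reference standard against which sensitivity, specificity, predictive values and AUC are calculated. If that standard closes a day before the condition does, some infants with the target condition are labelled free of it, and a correct alert for one of them counts as a false positive. If the standard has no closing time, sepsis from after 72 h, which Section 3 treats as a different condition with different risk factors, can count as a success or a miss for the model. Two analysts working from different sections would report different event counts and different accuracy from the same data.

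The 48 h rule also refers to when the diagnosis is recorded, whereas the Section 3 definition refers to when the infection presents. Delay between onset and senior review removes further cases.

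**Working it through.** **1. The definitions applied to three illustrative infants** (grade requirement taken as met):

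| Infant | Section 3 | Phase 3, Section 4.2 | Phase 3, Section 5 |
|---|---|---|---|
| Onset and diagnosis at 60 h | early-onset | case | non-case |
| Onset at 40 h, diagnosis recorded at 50 h | early-onset | case | non-case |
| Onset and diagnosis on day 5 | late-onset | case | non-case |

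Sections 4.2 and 5 disagree on all three. Section 4.2 departs from Section 3 on the third infant, and Section 5 departs from it on the first two. This needs no assumption about how common such infants are.

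**2. The plan's own event count.** Section 7.2.1 gives 900 participants in Phase 3, a clinical sepsis rate of 16% for the sample size, and a rate of 40.8% from a cited study. 900 × 0.408 = 367.2, which reproduces the stated 367 episodes. The sample-size rate gives 900 × 0.16 = 144. The section does not reconcile the two rates and gives neither a diagnostic window, so both are carried forward, treated as 72 h totals by assumption.

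**3. Cases miscoded under the 48 h rule.** Let f be the share of early-onset cases diagnosed at 48 to 72 h. The documents do not give it; 5% to 20% is assumed.

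| f | f × 144 | f × 367.2 |
|---|---|---|
| 5% | 7.2 | 18.4 |
| 10% | 14.4 | 36.7 |
| 20% | 28.8 | 73.4 |

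**4. Effect on accuracy, if the miscoded infants are flagged as often as other cases.** Take the plan's sensitivity of 90% and an illustrative specificity of 80% (assumption), with 144 true cases.

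- True positives: 144 × 0.90 = 129.6. False positives: (900 − 144) × 0.20 = 151.2. PPV = 129.6 / 280.8 = 0.46.
- At f = 5%: PPV = (136.8 × 0.90) / 280.8 = 0.44. Specificity = (604.8 + 7.2 × 0.10) / 763.2 = 0.79.
- At f = 20%: PPV = (115.2 × 0.90) / 280.8 = 0.37. Specificity = (604.8 + 28.8 × 0.10) / 784.8 = 0.77.

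With 367.2 true cases, PPV goes from 0.76 to 0.72 (f = 5%) or 0.61 (f = 20%). In each case PPV is multiplied by (1 − f).

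The 95% half-width for a sensitivity of 90% is 1.96 × √(0.09 / cases). It is 4.9 points with 144 cases and 5.5 points with 115.2.

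**5. The opposite extreme.** If the model flags none of the miscoded infants, PPV does not change, because they are not among the alerts. Sensitivity is then overstated: an apparent 0.90 among cases to 48 h corresponds to 0.90 × (1 − f) over 72 h, which is 0.86 at f = 5% and 0.72 at f = 20%. Which measure is distorted therefore depends on how the model scores these infants, which the 48 h outcome cannot show.

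**The case against.** **Sections 4.2 and 5 can be read together,** with 4.2 giving source and grade and 5 giving the window. That is a fair reading, and under it late-onset sepsis is kept out. But the protocol does not say so, the grades still differ, and the combined outcome still stops at 48 h for a 72 h condition.

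**The Phase 1 primary outcome and the model built on it are culture-based.** This stands. The 48 h clinician rule does not touch them. In Phase 1 it affects only secondary work on clinical diagnosis, such as the logistic regression for clinical sepsis. A reader might infer that predictor effects in the culture-based model are biased towards the null; that does not follow from this rule.

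**A reader might also infer that a single culture near delivery loses culture-positive cases.** The documents do not show this. Section 5 has the culture taken at birth in one place and allows it up to 48 h in another. Section 4.2 does not restrict a positive culture to the study sample. An early culture can detect an infection that presents later. The 5% culture-positive rate in Section 7.2.1 carries no sampling window, so it may already be an early-culture yield. What is missing is a rule on which cultures count; no number of lost events can be derived.

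**Transportability is already confounded,** because Phase 1 uses culture and Phase 3 uses clinician diagnosis, a difference that Section 5 discloses and explains. This also stands. Section 5 uses 48 h in both phases, so one window and one grade would remove an avoidable layer of difference, but not the main one.

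**Conclusion.** The inconsistency is real and certain on the text. Sections 3, 4.2 and 5 give three different time rules (72 h, none, 48 h) and three grade wordings, and the Phase 3 primary outcome is stated in two ways that can classify the same infant differently. Event count, sensitivity, PPV and AUC in the external validation depend on which section is followed.

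The size is not known. If 5% to 20% of early-onset cases fall at 48 to 72 h, 7 to 29 of 144 or 18 to 73 of 367 are miscoded. The proportional fall in PPV holds only if those infants are flagged as often as other cases; the accompanying fall in specificity is small at the 16% rate (0.80 to 0.77–0.79). The finding is confined to clinician diagnosis: the Phase 3 primary outcome and a Phase 1 secondary outcome. It does not show a loss of Phase 1 culture events.

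**What to change.** 1. Reconcile Sections 3, 4.2 and 5 to one clinician-diagnosed early-onset sepsis outcome: presentation by 72 h, one stated minimum grade, same wording in both phases. Record age at onset and age at diagnosis in hours, so that the 48 h version can be derived and reported as a sensitivity analysis.
2. Keep the universal study culture as the Phase 1 primary outcome, and say so in Section 4.2. Report clinical cultures taken by 72 h only as a sensitivity analysis. They are taken selectively in ill infants, and clinical signs are among the listed candidate predictors, so adding them to the primary outcome would make case-finding depend on the predictors.
3. For infants discharged before 72 h, use hospital record review where records are available, and add age at onset to the 28-day call. For infants seen elsewhere, the call now asks for the reason, any admission, the main diagnosis and treatment, but not age at onset or clinician grade.

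The cost is protocol and CRF wording, one added item in the call and some record review, with no new sampling or visits. The downside is that diagnoses made after discharge are less certain, and the clinician's grade may be unverifiable for infants seen elsewhere. The 48 h sensitivity analysis shows how far the results rest on them.

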2 RATIONALE

Current risk stratification systems are not able to predict neonatal sepsis risk in a low-resource setting with sufficient accuracy, as outlined in section 1. Reliable prediction of neonatal sepsis risk would enable clinicians to prioritise early broad-spectrum antibiotics and close monitoring for the highest-risk neonates, reducing associated morbidity and mortality, and allow earlier discharge of low-risk neonates without antibiotic treatment, reducing the economic and psychological burden to families of remaining in hospital and antimicrobial overuse. In a wider context, the ability to predict sepsis risk more accurately would also aid the development of clinical pathways and service planning within maternity and neonatal services. Finally, the resulting model and code from this study could be used by other researchers in the future to model risk of other infective conditions, or neonatal sepsis in other settings.

To build a model for risk stratification, data are required that encompass not only a broad range of potential risk factors for sepsis, but also accurate outcome data confirming or refuting the diagnosis of sepsis. Previous attempts to create risk stratification systems have lacked blood cultures as the gold standard diagnostic method for sepsis(20), so this study will include a blood culture sample from every participant. This study will also include a range of patient-reportable potential risk factors to maximise the clinical utility of the model in the future.

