Using machine learning to model early-onset neonatal sepsis risk in Uganda (NeoRisk)

- If attended elsewhere, the mother will be asked the reason for presenting, whether the neonate was admitted to hospital, the main diagnosis, and any treatments given.

Recruitment of the first 160 participants from labour ward (10% of the overall sample) will be treated as a pilot, and both recruitment and data will be reviewed at this point with particular attention to the following aspects:

- Demographic comparison between recruited women and the population attending Kawempe
- Data completion
- Volume of blood culture samples taken
- Loss to follow up rates
- Association between potential risk factors and clinical sepsis, or culture-positive sepsis

After this pilot analysis, the data collection instrument may be adjusted to be more concise if some risk factors appear to have no relationship with neonatal outcomes. Additionally, the recruitment strategy may be adjusted to include women attending antenatal clinics to improve the representativeness of the sample if the pilot sample is significantly different demographically to the general population of pregnant women attending the same study site antenatally. Finally, feedback and staff training will be given as needed to ensure optimal sample volumes and data completeness.

During Phase 1, two separate focus group discussions with 10 participants each will be held with staff from Kawempe Hospital. One discussion will be with senior clinicians, and one with junior clinicians and midwives. The focus groups will be held on site at Kawempe in English. Focus groups are being held in order to complement the quantitative results of this project by highlighting risk factors currently perceived as significant (which should then be a key part of analysis and results dissemination to confirm their usefulness), inform of current diagnostic difficulties to guide future work with the risk stratification model, and provide context for development and communication of the model to maximise its utility. The focus groups will address the following issues:

- Ascertain knowledge and awareness of neonatal sepsis
- Management of neonatal sepsis
- regarding risks and consequences of neonatal sepsis, and
- Current diagnostic strategies and their perceived strengths and difficulties
- Perceptions of neonatal sepsis and how this might affect diagnosis and treatment
- Recommendations to enhance the diagnosis and treatment of neonatal sepsis

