6 STUDY SETTING

Phase 1

Recruitment and data collection will take place at Kawempe Hospital in Kampala, Uganda. These sites are sufficiently busy to recruit the proposed sample size, have the necessary infrastructure to process blood cultures and have significant experience of running research studies within the labour and post-natal ward. Kawempe Hospital is a national referral hospital for high-risk pregnancies and local deliveries. Approximately 25,000 births occur at Kawempe annually, with approximately 11,000 neonatal admissions annually. Mulago Hospital is a large hospital with children's services(43). Electronic health records are currently used in both including antenatal and perinatal information, which are generated by digital data entry from paper hospital records. Blood cultures are currently processed at Makerere Microbiology Laboratories (College of American Pathologists accredited) using BACTEC machines within 12 hours of collection(43).

Phase 2

Data analysis and modelling will take place in collaboration with the Advanced Research Computing Centre at University College London.

Phase 3

Recruitment and data collection will take place at Sally Mugabe Central Hospital in Harare, Zimbabwe. Again, this site is large enough to recruit the proposed sample size, with 22,000 births annually, and has existing research infrastructure to enable quality data collection(41). The Neotree platform is in routine use at Sally Mugabe Central Hospital.

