7.2 Sampling

7.2.1 Size of sample

Phase 1: There is currently no accepted way to power a machine learning study, the consensus being that more data will always create a better model. However, to ensure the success of this study, we have investigated approximate power to create a diagnostic test to estimate the sample size needed for this study. We have also reviewed this sample size calculation with our collaborators at the UCL Advanced Research Computing centre.

A study of a diagnostic test with 90% sensitivity and a background sepsis rate of 5% (the estimated rate of culture-positive sepsis in Kampala based on previous studies is 12.8%(13) amongst those with clinical signs of sepsis, and up to 5% amongst all neonates according to unpublished data from previous studies at Kawempe) would require 1460 participants (95% confidence interval), as described by Buderer and Jones *et al*(45,46).

This sample size has also been calculated according to three suggested methods for calculating the sample size for a clinical prediction model:

- Calculation of size needing to provide precise estimate of overall outcome risk
- Calculation of size needed to produce predicted values with a small mean error across all individuals
- Size needed considering shrinkage of predictor effects

All of the above methods produced sample sizes from 140-1532, hence the size of 1600 should be sufficient even with some loss to follow up. If, at interim analysis, the rate of culture-positive sepsis is significantly lower, we will explore methods to increase our sample size such as using existing data to create simulated data to train our model.

Phase 3: The sample size will be 900 mothers; this is powered to give 95% confidence for a diagnostic test which has 90% sensitivity with a background rate of clinical sepsis of 16%, using the same calculation method as for the sample size in Phase 1. Although there are limited previous studies of neonatal sepsis prevalence in Zimbabwe using blood cultures, particularly amongst all neonates, one study found a culture-positive sepsis rate of 21% amongst NICU admissions(47), and a recent study reported a clinical diagnosis rate of 40.8%(48) . Therefore, this sample size should give an estimated 367 episodes of clinician-diagnosed sepsis, deemed by Collins *et al.* to be sufficient for external validation of a prognostic model(49).

Using machine learning to model early-onset neonatal sepsis risk in Uganda (NeoRisk)

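### The pilot rule lets data fields be dropped for showing no relationship with outcomes after 160 infants, which is too few to show that a relationship is absent

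*Combined protocol and SAP*

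**What the plan says.** Section 5 (Phase 1) treats the first 160 labour-ward recruits, 10% of the sample, as a pilot. Five items are reviewed. One is "Association between potential risk factors and clinical sepsis, or culture-positive sepsis"; the others are demographic comparison, data completion, culture volume and loss to follow-up. The consequence for the case report form (CRF) is that "the data collection instrument may be adjusted to be more concise if some risk factors appear to have no relationship with neonatal outcomes".

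No criterion is given for judging that a relationship is absent: no test, interval, effect size or minimum number of cases. Section 5 refers to section 7.3 for detail on the interim analysis, but 7.3 covers only how representative the sample is and whether to recruit from antenatal clinics. Section 7.2.1 sizes the full study, not the pilot. It puts the culture-positive rate at "up to 5% amongst all neonates according to unpublished data from previous studies at Kawempe".

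Two other passages bear on the point. The table in section 3 marks candidate factors as Established or Investigational. The focus groups in section 5 are meant to help by "highlighting risk factors currently perceived as significant (which should then be a key part of analysis" and of dissemination).

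**The concern.** The clause treats a lack of visible association in a small sample as evidence that a factor does not matter. With a handful of cases, most factors will show no clear association, including some that matter.

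Objectives 1 and 2 are to determine risk factors and to build a model from them. Section 2 says: "This study will also include a range of patient-reportable potential risk factors to maximise the clinical utility of the model in the future". Section 3 (machine learning) hopes for associations nobody has yet noticed. The factors marked Investigational are therefore the ones the study most wants to learn about, and they are also the most exposed to this clause because no prior evidence argues for keeping them.

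The loss is hard to reverse. Under section 7.3.3, data come from health records and, where needed, from interviews. A field held in the records might be re-extracted later. A field that exists only through interview, which probably includes household items such as handwashing access, could not easily be recovered. It would be available for the pilot infants and for few others.

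**Working it through.** **Inputs from the protocol**
- Phase 1 sample 1600; pilot 160 (section 5).
- Culture-positive rate 5%, given as an upper figure (section 7.2.1).
- Clinical sepsis rate 16%: the Phase 3 planning value (section 7.2.1), used here as an assumption because no figure for all Kawempe births is given.

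**Assumptions not in the protocol:** a binary factor with exposure *f* of 10%, 30% or 50%, and a true OR of 2 for the power check.

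**Step 1. Pilot size and cases.** 0.10 × 1600 = 160, as stated. Expected culture-positive infants: 160 × 0.05 = 8 (95% binomial range 3 to 14). Because 5% is an upper figure, the number may be lower: 160 × 0.03 = 4.8, or 160 × 0.02 = 3.2.

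**Step 2. What a perfectly null pilot result would exclude.** Take an observed OR of exactly 1, with cell counts at their expected values. Woolf's variance of the log OR is

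var = [1/(fp) + 1/((1−f)p) + 1/(f(1−p)) + 1/((1−f)(1−p))]/n = 1/[n f(1−f) p(1−p)]

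and the 95% interval is exp(±1.96 × SE). For p = 5% and f = 30%: 1/(160 × 0.21 × 0.0475) = 0.627, SE = 0.792, interval 0.21 to 4.7.

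| Outcome rate p | Exposure f | SE | 95% CI at observed OR 1 |
|---|---|---|---|
| 5% (culture-positive) | 10% | 1.209 | 0.09 to 10.7 |
| 5% | 30% | 0.792 | 0.21 to 4.7 |
| 5% | 50% | 0.725 | 0.24 to 4.1 |
| 16% (clinical, assumed) | 10% | 0.719 | 0.24 to 4.1 |
| 16% | 30% | 0.471 | 0.40 to 2.5 |
| 16% | 50% | 0.431 | 0.43 to 2.3 |

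No row excludes a doubling of the odds. The first row rests on 160 × 0.10 × 0.05 = 0.8 expected exposed cases, so it shows only the order of magnitude.

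**Step 3. Chance of detecting a real factor.** Risks p0 (unexposed) and p1 (exposed) are chosen so that the OR is 2 and f·p1 + (1−f)·p0 = p. At p = 5% and f = 30% this gives p0 = 3.91% and p1 = 7.53%. Power of Fisher's exact test at two-sided 0.05 with 160 infants, letting the number exposed vary by chance:
- culture-positive sepsis: about 10% to 14% for exposures of 10% to 50%;
- clinical sepsis at 16%: about 19% to 32%.

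Fixing the exposed group at its expected size (exposures of 10%, 25% and 50%) gives 7% to 15% for culture-positive sepsis, which leads to the same conclusion.

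**Step 4. How much data would be needed.** At p = 5% and f = 30%, the upper limit at an observed OR of 1 falls to 2 when n = 100.25/(ln 2/1.96)² = 802, or about 40 culture-positive infants. That is half the full sample and five times the pilot.

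**Step 5. What a cut would cost.** A field removed after the pilot could be missing for up to 1600 − 160 = 1440 infants. The number is smaller if recruitment continues while the pilot is reviewed.

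**The case against.** The clause says only that the form may be adjusted. Nothing commits the team to cutting any field, and association is one of five review items. This stands: the harm is conditional. But the ground the clause names is one the pilot cannot establish, and nothing elsewhere narrows it.

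The clause speaks of neonatal outcomes generally, and section 4.2 lists commoner ones such as "Admission to neonatal unit". A commoner outcome would give tighter intervals. However, the protocol gives no admission rate for eligible infants. The hospital-wide counts in section 6 do not supply one, because infants under 34 weeks are admitted automatically and are excluded here (section 7.1.2). Nor is admission the Phase 1 primary outcome.

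Safeguards exist. Established factors have a rationale for staying whatever the pilot shows, although the table is not made a protected list. The focus groups help factors that staff already suspect, but they are timed only as during Phase 1 and do nothing for unsuspected ones. Section 8.2 requires amendments to be approved but does not say whether removing a field counts as one.

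A reader might go further and infer that the plan will lose some definite share of real predictors. The documents do not support that: they state no cut rule, so any such share would depend on a rule the reader supplied. A reader might also infer that the pilot association review is itself improper. It is not; it is sound as description, and the fault lies in using it to remove fields.

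**Conclusion.** The point holds as a contained design weakness. The clause permits, but does not require, removing fields on evidence that cannot support the decision. With at most about 8 expected culture-positive infants, even an exactly null pilot result is compatible with a true OR above 4 at 30% to 50% exposure. On clinical sepsis, at the borrowed 16% rate, it is compatible with an OR above 2. A factor that doubles the odds would usually fail to show.

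These sizes rest on the assumed exposures, a single unadjusted binary factor, the upper 5% rate and the Phase 3 clinical rate. A lower culture-positive rate makes the position worse. A higher clinical sepsis rate in Kampala would improve the clinical figures. Which fields exist only through interview is also an inference, since the protocol does not list them. The change should be made because a cut is hard to undo and the correction is cheap.

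**What to change.** In section 5, delete apparent lack of association with outcomes as a reason to shorten the form. Replace it with text to this effect:

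> After the pilot, fields may be removed only on grounds judged without reference to outcome: missingness, redundancy with another field, interview burden, or no useful variation. Factors marked Established in section 3 will not be removed for low prevalence in the pilot. Pilot associations between factors and sepsis will be summarised descriptively and will not be used to remove fields.

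The second sentence is needed because a factor with 2% prevalence would have only about 3 exposed infants (0.02 × 160 = 3.2). A variation rule could therefore discard rare but recognised factors on equally thin evidence.

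An alternative is to keep an association rule but set it in advance, with a minimum number of cases and an interval that must exclude a stated OR. If that OR were 2, none of the settings in the table above would meet it at 160 infants, so deletion is simpler.

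The cost is wording only. The downside is a somewhat longer form after the pilot and some extra interview time per mother.
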